**The Effects of temporary ileostomy on outcome in
patients with rectal cancer, A prospective
Comparative Cohort Study protocol**

NCT number: not available yet

Date: 10/9/2021

Background

Colorectal cancer(CRC) represents the most common type of gastrointestinal cancer [1]. It is the third most commonly diagnosed cancer in males and the second in females according to the World Health Organization (WHO), with various rates of incidence around the world [2]. CRC is a multifactorial disease process that includes genetic factors, environmental exposures, and inflammatory diseases [3]. There is an improvement in outcome and death rates have declined progressively which can be attributed to early detection and removal of CRCs in earlier stages and effective adjuvant therapy [4]. Surgery is considered currently the definitive treatment modality for rectal cancer, and surgical intervention is performed either by local or radical excision depending on the clinical stage, size, and location of the primary tumor [5].

There are many techniques to be used including local excision, low anterior resection(LAR), abdominoperineal resection, and multi-visceral resection [6]. LAR represents a sphincter-sparing resection and is performed in patients who meet all the following criteria: invasive rectal cancer, the ability to perform negative distal margin, and an adequate anorectal sphincter function before surgery [7]. Numerous postoperative complications can significantly lead to morbidities, prolonged hospitalization, and even mortality, and management of these complications can be beneficial for survival rate and improvement of quality of life [7]

Anastomotic leakage(AL) represents a frequent complication after LAR in patients with rectal cancer and is responsible for significant morbidity and mortality. The incidence of AL varies from 3 to 21% with a high rate of mortality despite improvements in

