surgical techniques [8]. In addition, AL is associated with worsened functional outcomes, reduced quality of life, and increased financial burden. Risk factors for AL include more distal anastomoses, neoadjuvant pelvic radiation therapy, male gender, prolonged operative time, advanced stage of tumor, and multiple firings of linear stapler across rectal stump [9]. The role of a protective stoma has been debated. Therefore, the aims of our study were: 1- to evaluate the effect of temporary ileostomy on the occurrence of AL, 2-to compare complications between patients according to the presence of protective ileostomy.

Methodology

Patients

This is a prospective comparative study of a group of patients with a diagnosis of colorectal cancer of both sexes and all ages that required low anterior resection(LAR) attending the Department of General Surgery at Tishreen University Hospital in Lattakia-Syria during the two years (May 2021- May 2023). The exclusion criteria are patients who undergo abdominoperineal resection with permanent ileostomy. The following workup included: a history and physical examination.

Preparation of the bowel is performed before surgery with the administration of intravenous perioperative antibiotic prophylaxis. The surgical procedure is performed by laparotomy, with resection of the rectum and mesorectum (TME) up to the level of the pelvic diaphragm, sparing the autonomic nerves. End-to-end anastomosis is performed either with a stapler or by hand-sewn. Patients are assigned to group I (19 patients) who will undergo temporary ileostomy, and group II (28 patients) who will not undergo ileostomy. Patients are followed up at regular intervals and outcomes were compared between two groups.

Data collection

the following data will be collected through clinical examinations, patient interviews, and medical records including : Demographic data including : Age as Continuous variable measured in years, Sex as Categorical variable (Male/Female), Tumor Stage as Categorical variable representing the clinical stage of colorectal cancer, Radiotherapy as Binary variable indicating whether the patient received radiotherapy before surgery. The Surgical Characteristics are : the Type of Anastomoses as

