Categorical variable (Hand-sewn/Stapled), and Protective Ileostomy as Binary variable indicating the presence or absence of a temporary ileostomy. The Outcomes which will be measured are : the Duration of Surgery as Continuous variable measured in hours, the Anastomosis Leakage as Binary variable indicating the presence or absence of leakage, the Surgical Site Infection as Binary variable indicating the presence or absence of infection, and the Local Recurrence as Binary variable indicating the presence or absence of local recurrence.

Patients will be followed for 30 days after surgery to assess short-term outcomes. Assessments will be conducted at regular intervals to monitor the occurrence of outcomes.

Ethical Considerations

Written informed consent will be obtained from the patient for publication and any accompanying images. A copy of the written consent is available for review on request. Ethical approval for this study (Ethical Committee 2021-GS-104) was provided by the Ethical Committee of Tishreen University Hospitals, Latakia, Syria on 10 October 2021. In addition, the investigators ensure that the study conforms to the principles of the Declaration of Helsinki (last revised in 2013) and is conducted in accordance with the ICH Guideline for Good Clinical Practice.

Statistical Analysis Plan

Statistical analysis was performed by using the IBM SPSS version. Basic Descriptive statistics included means, standard deviations(SD), median, Frequency, and percentages. To examine the relationships and comparisons between the two groups, the chi-square test was used. Independent t student tests were used to compare 2 independent groups. All the tests were considered significant at a 5% type I error rate($p<0.05$), $\beta:20\%$, and power of the study:80%.

References

1-Saltz L. Top advances of the year in colorectal cancer. *Cancer* 2022;128:2236-2239.

2-WHO. Cancer. Available online: [https://www.who.int/news-room/fact-sheets/detail/cancer\(2021\)](https://www.who.int/news-room/fact-sheets/detail/cancer(2021)).

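### Leakage, the first aim, gets a chi-square p-value but no effect estimate or confidence interval, so a non-significant result in 19 vs 28 patients would say little

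*Combined protocol and SAP*

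**What the plan says.** The aims, at the end of the Background, are first "to evaluate the effect of temporary ileostomy on the occurrence of AL" and second "to compare complications between patients according to the presence of protective ileostomy". The Data collection section defines the main outcome as "the Anastomosis Leakage as Binary variable indicating the presence or absence of leakage". The Patients section gives 19 patients with ileostomy and 28 without, and describes no randomisation.

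The Statistical Analysis Plan is one paragraph. On description it says: "Basic Descriptive statistics included means, standard deviations(SD), median, Frequency, and percentages". On comparison: "To examine the relationships and comparisons between the two groups, the chi-square test was used". It adds independent t tests, which do not apply to leakage, and a decision rule: "All the tests were considered significant at a 5% type I error rate". It also states 80% power, with no effect size or leak rates attached. The protocol and SAP name no between-group effect measure, regression model or confidence interval, and do not say which version of the chi-square test is meant. The only leak rate given is general background: "The incidence of AL varies from 3 to 21" percent.

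**The concern.** An aim to evaluate an effect calls for an estimate of that effect and its uncertainty. The plan yields two percentages and a verdict of significant or not. With few leaks expected, the likely verdict is not significant, and the plan has no measure of how large a difference in either direction the data still allow. The bare 80% power statement adds to the risk, because it suggests that a negative result would be informative. At low leak rates there is also a real chance that no patient leaks; the chi-square is then undefined and the plan gives no between-group inference.

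**Working it through.** **Inputs.** Group sizes 19 and 28 (Patients section). Significance level 5% (SAP), taken as two-sided because the SAP does not say. Leak rates of 3% to 21% (Background). Applying that range to these groups, and every pairing of rates below, is an assumption.

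**The plan's own figure.** The stated 80% power cannot be reproduced, because no rates are attached to it. The first table below shows what the group sizes give.

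**Expected leaks** (n × rate)
- Ileostomy: 19 × 0.03 = 0.57 to 19 × 0.21 = 3.99.
- No ileostomy: 28 × 0.03 = 0.84 to 28 × 0.21 = 5.88.

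**Chance of p<0.05.** All 20 × 29 = 580 possible tables were enumerated with binomial probabilities and the uncorrected Pearson test.

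| True rate, ileostomy vs none | Chance of p<0.05 |
|---|---|
| 3% vs 3% | 0.8% |
| 10% vs 10% | 3.3% |
| 21% vs 21% | 4.8% |
| 3% vs 15% | 14.8% |
| 10% vs 21% | 14.5% |
| 3% vs 21% | 38.4% |
| 21% vs 3% (reverse direction) | 50.8% |

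The equal-rate rows show that Pearson does not inflate false positives at these rates. The 38.4% is the maximum within 3–21% when ileostomy has the rate that is no higher.

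**One table worked through: 1/19 vs 5/28**
- Risk difference: 0.0526 − 0.1786 = −0.1259.
- Pearson: pooled rate 6/47 = 0.1277. X² = 0.1259² / [0.1277 × 0.8723 × (1/19 + 1/28)] = 1.61, p = 0.20.
- Wilson 95% limits: 0.0094 to 0.2464 (ileostomy) and 0.0788 to 0.3559 (none).
- Newcombe lower limit: −0.1259 − √[(0.0526 − 0.0094)² + (0.3559 − 0.1786)²] = −0.308.
- Newcombe upper limit: −0.1259 + √[(0.2464 − 0.0526)² + (0.1786 − 0.0788)²] = +0.092.

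**Other tables by the same formulas**

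| Leaks, ileostomy vs none | Pearson p | Risk difference, points (95% CI) |
|---|---|---|
| 0/19 vs 5/28 | 0.051 | −17.9 (−35.6 to +1.7) |
| 2/19 vs 4/28 | 0.70 | −3.8 (−22.6 to +18.8) |
| 0/19 vs 0/28 | undefined | 0.0 (−12.1 to +16.8) |

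**How typical this is.** There are 66 tables with 10 or fewer leaks, and 42 of them are not significant (counting 0 vs 0). Their intervals are 29 to 48 points wide, and 23 of the 42 contain both a 10-point reduction and a 10-point increase. Ten points is only an illustration. Weighted by probability, the share of non-significant studies with such an interval is 67–77% at equal rates of 3–21%, 62% at 3% vs 10%, 45% at 3% vs 15% and 30% at 3% vs 21%.

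**No leaks at all.** 0.97⁴⁷ = 23.9% of studies at 3%, 0.95⁴⁷ = 9.0% at 5%, 0.90⁴⁷ = 0.7% at 10%.

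**Secondary: which chi-square.** Eight tables with 10 or fewer leaks change verdict between Pearson, continuity-corrected and Fisher. For 0/19 vs 6/28 the p-values are 0.031, 0.086 and 0.068. Versions disagree in 0.7–3.2% of studies at equal rates and in 24.3% at 3% vs 21% (13.6% for Pearson against Fisher alone).

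**The case against.** The strongest reply is that little information is lost. Percentages will be reported and the group sizes are known, so any reader can subtract and compute an interval. That is true: the gap lies in what the authors commit to report and how they will read it, not in the data or in a wrong test. But leaving the estimate to readers does not meet the first aim, and it does not stop the authors from treating p≥0.05 as absence of effect.

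Several qualifications stand.
- The share of intervals reaching 10 points both ways falls as the true difference grows, and two of the three worked non-significant tables with leaks do not reach +10.
- The 38% applies when ileostomy lowers leakage; in the reverse direction the figure is 50.8%.
- Counts of tables are not probabilities, and the cut at 10 leaks omits 40% of studies at 21% in both groups.
- The zero-leak problem matters only at low rates.
- Which version of the test to name is partly a matter of preference; an exact test could also be argued for.
- The comparison is not randomised, so the interval covers sampling error only.
- The SAP is written in the past tense, the group sizes are already exact, and a document dated 2021 cites a 2022 reference. True pre-specification may therefore no longer be possible.

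None of these removes the omission.

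**Conclusion.** The concern holds. The plan has no effect estimate or interval for its first aim, and with 19 and 28 patients the p-value cannot stand in for one. For a benefit within the quoted 3–21% range, the chance of significance is at most 38%. Non-significant tables with 10 or fewer leaks carry intervals 29 to 48 points wide. This rests on assumed leak rates, two-sided testing at 5% and the uncorrected Pearson test; the omission itself rests on no assumption. The planned test is not invalid, so this is an inexpensive improvement that should be made rather than a fatal fault. The unnamed test version is a lesser point. The figures cover leakage only, because the documents give no rates for infection or recurrence.

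**What to change.** Keep the chi-square sentence for categorical variables and add:

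> For leakage and the other binary outcomes, the risk difference (ileostomy minus none) with a Newcombe 95% confidence interval is reported with the p-value. The p-value comes from one test named in advance (uncorrected Pearson chi-square), which decides significance. If no event occurs in either group, no test is done and the interval alone is reported. A non-significant result is interpreted from the interval, not as absence of effect. The interval is unadjusted and does not address confounding.

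If outcomes have already been seen, the addition should be labelled as made afterwards.

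**Cost.** Five sentences and no new data; the interval is a closed formula from four counts. Its coverage is 99.9% at 3% in both groups, 97.8% at 10%, 95.9% at 21%, and 96.6% at 3% vs 21%.

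**Downsides.**
- Test and interval disagree on two tables with 10 or fewer leaks: 1/19 vs 8/28 (p=0.046, interval −42.3 to +0.2) and 3/19 vs 0/28 (p=0.030, interval −0.05 to +37.6). This happens in 0.6–1.4% of studies at equal rates, at most 4.0% if ileostomy has the lower rate, and up to 10.4% if it has the higher (16% vs 3%). That is why the text says the test decides.
- Wide intervals will make the conclusions more cautious.
- Confounding remains to be handled separately.

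### The Student t test named for continuous variables holds its 5% level only if the two variances are equal; with groups of 19 and 28, pre-specifying Welch removes that assumption at almost no cost

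*Combined protocol and SAP*

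**What the plan says.** The Statistical Analysis Plan names one method for comparing means: "Independent t student tests were used to compare 2 independent groups". The level applies to everything: "All the tests were considered significant at a 5% type I error rate". The Patients part of the Methodology section gives the sizes: "Patients are assigned to group I (19 patients) who will undergo temporary ileostomy, and group II (28 patients) who will not undergo ileostomy".

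Two continuous variables are listed under Data collection. One is an outcome, "the Duration of Surgery as Continuous variable measured in hours", and the other is a baseline variable, "Age as Continuous variable measured in years". Leakage, surgical site infection and local recurrence are all binary.

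The plan does not mention an unequal-variance version of the test, a variance check, a transformation or a rank-based alternative. It gives no SD for either continuous variable and does not say whether tests are two-sided.

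**The concern.** The equal-variance t test estimates one common variance, and in doing so gives more weight to the larger group. If the smaller group is the more variable one, the standard error is too small and the test rejects too often. If the larger group is more variable, the standard error is too large and the test is conservative. With equal group sizes the effect nearly cancels; with 19 and 28 it does not.

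Nothing in the documents supports assuming equal variances. Groups are defined by whether a stoma is formed, no randomisation is described, and the anastomosis may be stapled or hand-sewn. The ileostomy group also has an extra operative step. A difference in the spread of operating time is therefore possible. If there is one, the p-value for the only continuous outcome does not have the 5% error that the plan states for it.

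**Working it through.** **Inputs from the documents.** n₁ = 19 (ileostomy), n₂ = 28 (no ileostomy), α = 0.05.

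**Assumptions.** Two-sided testing; normal data unless stated; SD ratio r = SD₁/SD₂, varied because no SD is given; Student read as the equal-variance (pooled) test with 19 + 28 − 2 = 45 degrees of freedom.

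**Step 1: the plan's own figure.** At r = 1 the pooled test has an error of exactly 5.0%. The stated level is reproduced, on the condition of equal variances.

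**Step 2: why the level moves.** Take SD₂ = 1.

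- Expected pooled variance of the mean difference: [(18r² + 27)/45] × (1/19 + 1/28)
- True variance of the mean difference: r²/19 + 1/28

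With 1/19 + 1/28 = 0.0883:

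- r = 2: pooled (72 + 27)/45 × 0.0883 = 0.194; true 4/19 + 1/28 = 0.246. Ratio 0.79, so the standard error is about 11% too small (√0.79 = 0.89).
- r = 0.5: pooled (4.5 + 27)/45 × 0.0883 = 0.062; true 0.25/19 + 1/28 = 0.049. Ratio 1.27, so the standard error is about 12% too large (√1.27 = 1.12).

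**Step 3: actual type I error.** The rejection probability was found by numerical integration over the two sample variances. The Welch test used Satterthwaite degrees of freedom. Simulation with 400,000 data sets per scenario, at ratios of 0.5, 1, 1.5, 2 and 3, agreed to within about 0.1 point.

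| SD ratio r | Student (pooled) | Welch |
|---|---|---|
| 0.5 | 3.0% | 5.0% |
| 0.67 | 3.6% | 5.0% |
| 0.8 | 4.1% | 5.0% |
| 1 | 5.0% | 5.0% |
| 1.25 | 6.0% | 5.0% |
| 1.5 | 6.9% | 5.0% |
| 2 | 8.3% | 5.0% |

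From r = 0.25 to r = 4 Welch lies between 4.97% and 5.03%.

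**Step 4: cost in power at equal variances.** The plan states 80% power without an effect size. With 19 and 28 patients, 80% for the pooled test corresponds to a standardised difference d of 0.85.

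- d = 0.5: 37.7% Student, 37.4% Welch
- d = 0.8: 75.0% and 74.6%
- d = 0.85: 80.0% and 79.7%
- d = 1.0: 90.9% and 90.6%

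The largest loss at the values tried is 0.37 points.

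**Step 5: power at unequal variances.** At r = 0.5 and a true difference of 0.5 SD₂, Welch has 59.8% against 50.5%. At r = 2 and a difference of 1 SD₂, Welch has 49.0% against 59.3%, but the Student figure comes from a test whose error is 8.3%.

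**Step 6: choosing the test after looking at the variances.** An F test at 5% detects r = 1.5 only 47% of the time. Picking Student or Welch by its result gives 5.7% error at r = 1.5, so choosing Welch in advance is cleaner.

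**Step 7: skewed data.** With lognormal durations, equal means and SDs of 0.66 and 0.31 (ratio about 2.1, the smaller group more variable), Student gives 9.5% and Welch 6.9%.

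**The case against.** The strongest reply is that the larger figures do not follow from the obvious mechanism. Suppose the stoma step adds time independent of the rest of the operation, and let s be the SD of that step divided by the SD of the rest. Then r = √(1 + s²). A ratio of 1.5 needs s = √1.25 = 1.12, and a ratio of 2 needs s = √3 = 1.73. The stoma step would have to vary more than the whole laparotomy, resection and anastomosis. At smaller values:

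- s = 0.25: r = 1.03, error 5.1%
- s = 0.5: r = 1.12, error 5.5%
- s = 0.75: r = 1.25, error 6.0%

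This stands. On that mechanism the inflation is at most about one point. Independence is itself an assumption, and a different mix of cases or techniques could move the ratio either way. A selected ileostomy group could also be less variable, which makes the Student test conservative.

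A reader might infer that the 5% level is not kept in this study, or that its true error is 7% to 8%. The documents support neither: they contain no SD, and at equal variances the level is exact.

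Two further replies also stand. The stated aims are leakage and complications, which use binary outcomes and not the t test. And the plan never says pooled; that is inferred from the name Student. If an unequal-variance test was meant, the text still needs to say so.

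**Conclusion.** The point holds as a conditional one. The named test delivers the stated 5% only under equal variances, which the plan neither states nor justifies, and the group sizes of 19 and 28 make it sensitive to that. For modest differences in spread (ratios of 0.8 to 1.25) the error is 4.1% to 6.0%. Larger departures, from 3.0% at a ratio of 0.5 to 8.3% at 2, need SD ratios for which the documents offer no evidence. All these figures assume normal data and two-sided tests.

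One outcome, duration of surgery, and one baseline comparison, age, are concerned. It would be wrong to read this as a doubt about the leakage comparison. Nor is Welch a complete remedy: it removes the equal-variance assumption, but strong skewness combined with unequal spread can still lift its error above 5%. The importance is small and the change is worth making because it is so cheap.

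**What to change.** In the Statistical Analysis Plan, replace the independent Student t test with the Welch (unequal-variance) t test for continuous variables. State that it is used whatever the observed variances, and that tests are two-sided. Report the mean difference in duration of surgery with its Welch 95% confidence interval; the plan currently mentions no interval.

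A sensitivity analysis on the log scale may be added in case durations are strongly skewed. It compares geometric means, so it should be labelled as answering a slightly different question.

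The cost is a sentence or two in the plan and 0.3 to 0.4 points of power if the variances are in fact equal. No extra patients or data are needed.

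### Leakage is the first aim, but the outcome list and analysis plan name no primary outcome, so any of four tests at 5% can be presented as the study's ileostomy effect

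*Combined protocol and SAP*

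**What the plan says.** The Background closes with two numbered aims. The first is "to evaluate the effect of temporary ileostomy on the occurrence of AL"; the second is a comparison of complications by ileostomy status. Neither is called primary.

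The Data collection section then lists four outcomes without ranking them. It opens with "The Outcomes which will be measured are : the Duration of Surgery as Continuous variable measured in hours". Leakage comes second, infection third and recurrence last, each recorded as a yes/no variable. Follow-up is 30 days.

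The Statistical Analysis Plan names the chi-square test and the independent t test and sets one threshold for everything: "All the tests were considered significant at a 5% type I error rate". Beside it stands one power statement, "power of the study:80" per cent, which is tied to no outcome, effect size or sample size. The plan gives no testing order, no adjustment and no rule for how the four results combine into a conclusion. It does not say whether the chi-square is continuity-corrected or whether tests are two-sided.

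**The concern.** The order of the aims shows which outcome matters most, but neither the outcome list nor the analysis plan carries that order over. Followed as written, a nominally significant difference in infection or operating time has the same standing as the leakage result. The second aim, on complications, is broad enough to cover a headline on an outcome other than leakage.

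The gap matters more because the leakage comparison is weak at 19 v 28. A null result for leakage beside one p<0.05 elsewhere is a realistic report, and the plan gives the reader no way to tell which result answers the study question. The power figure has a similar problem: power belongs to a particular comparison, and none is named.

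**Working it through.** **The plan's own figures.** The 5% is a chosen per-test threshold, so there is nothing to derive; it is right for any one test taken alone. The 80% power cannot be reproduced, because the plan gives no event rates, difference or standard deviation.

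**Inputs.**
- From the plan: 19 patients with and 28 without ileostomy; leakage incidence 3-21% (Background); chi-square for binary outcomes, t test for duration; p<0.05.
- Assumed: infection 10-30%; recurrence within follow-up 0-2%; two-sided tests; independent outcomes; t test with true size 5%.

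**Step 1, nominal ceiling.** Four independent tests, each of exact size 5%, give 1 − 0.95^4 = 18.5%. This is too high here, because a chi-square test on sparse events in 47 patients rejects less often than 5%.

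**Step 2, actual size of each binary test.** With the same event rate p in both groups, sum the product of the two binomial probabilities, (19, p) and (28, p), over all tables with p-value below 0.05:

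| Event rate | Uncorrected | Continuity-corrected |
|---|---|---|
| 2% | 0.35% | 0.03% |
| 3% | 0.79% | 0.09% |
| 10% | 3.25% | 0.86% |
| 21% | 4.77% | 1.69% |
| 30% | 4.64% | 2.13% |

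**Step 3, at least one false positive.** The formula is 1 − (1 − size of t test) × product of (1 − size of each binary test).

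Low end (leakage 3%, infection 10%, recurrence 0%):
- Uncorrected: 1 − 0.95 × 0.9921 × 0.9675 = 8.8%.
- Corrected: 1 − 0.95 × 0.9991 × 0.9914 = 5.9%.

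High end (leakage 21%, infection 30%, recurrence 2%):
- Uncorrected: 1 − 0.95 × 0.9523 × 0.9536 × 0.9965 = 14.0%.
- Corrected: 1 − 0.95 × 0.9831 × 0.9787 × 0.9997 = 8.6%.

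The uncorrected size peaks at a rate slightly above 20%, so infection at 20% instead of 30% gives 14.1%. The rounded range does not change.

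**Step 4, without duration.** Dropping the factor 0.95 gives 4.0% to 9.5% uncorrected (9.6% with infection at 20%) and 1.0% to 3.8% corrected.

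**Step 5, power for leakage.** Take the widest contrast that the cited range allows, 3% with and 21% without ileostomy. The same enumeration, with different rates in the two groups, gives exact power of 38% uncorrected and 14% corrected, against the stated 80%.

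**The case against.** The strongest reply is that the plan states a per-test threshold and nothing more. A reader might infer that the stated 5% is false, or that the study runs at an 18.5% error rate. The documents support neither. They claim no family-wise rate and contain no rule that one significant outcome makes the study positive, and a per-comparison threshold can properly apply to each test. This stands, and it limits the point to what the plan allows, not what it asserts.

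Second, leakage already has a special place as the first aim, and the outcome list describes variable types without claiming to rank them. This also stands in part: the intended primary outcome can be guessed. But it is not written where the analysis is specified, so the guess binds nobody.

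Third, the inflation is modest and depends on choices the plan leaves open. With continuity correction and without duration, the chance of a false positive stays below 5%. Much of the excess comes from the duration test, and if making an ileostomy does change operating time, a significant duration result is not a false positive at all. Recurrence adds almost nothing. Positive correlation between outcomes would lower the figures further. All of this is correct, and it is why ranges are given and not one multiple of 5%.

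Finally, whether secondary outcomes need a formal multiplicity procedure is a matter of convention. The point does not depend on it: naming one primary outcome needs no correction.

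**Conclusion.** The point holds as a gap in specification. Four outcomes have equal standing, each is tested at 5%, and nothing stops any one of them from carrying the ileostomy conclusion, although the aims put leakage first.

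Over all four tests the chance of at least one false positive is about 9-14% (uncorrected) or 6-9% (corrected). Over the three binary outcomes it is 4-10% or 1-4%, so an excess over 5% is not certain there. These figures rest on independent outcomes, two-sided tests and infection and recurrence rates that the plan does not give. They cover chance alone, not imbalance between groups in a non-randomised comparison.

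Two stronger readings should be avoided. The plan does not misstate its type I error, since it states only a per-test rate. Nor can the missing primary outcome be repaired by assigning the 80% power to leakage: at 19 v 28 the design delivers about 38% (14% corrected) even for 3% v 21%.

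**What to change.** In the Statistical Analysis Plan, and matching it in the outcome list:

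- State that anastomotic leakage within the 30-day follow-up is the single primary outcome, tested once at two-sided 5%, and say which version of the chi-square is used.
- Label duration of surgery, surgical site infection and local recurrence as secondary. Report them as between-group differences with 95% confidence intervals, not as confirmatory findings.
- Remove the 80% power figure, or replace it with one calculated for leakage from stated rates at 19 v 28. Do not attach the present figure to leakage.

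The labelling takes two sentences, needs no extra patients and costs the leakage test no power. By comparison, a Bonferroni split over four outcomes (0.05 / 4 = 1.25% each) would cut exact power for 3% v 21% from 38% to 13% with the uncorrected test. The price is that a secondary p<0.05 can no longer be presented as a confirmed effect, and that the plan must drop its power claim or report a much lower one.

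### The stated 80% power belongs to no outcome, rate or difference, and is unsupported for anastomotic leakage with 19 and 28 patients

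*Combined protocol and SAP*

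**What the plan says.** The Statistical Analysis Plan names two test families. For group comparisons, "To examine the relationships and comparisons between the two groups, the chi-square test was used"; and "Independent t student tests were used to compare 2 independent groups". Its last sentence begins "All the tests were considered significant at a 5% type I error rate", then gives beta as 20% and ends "and power of the study:80" (per cent).

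The outcomes are listed under Data collection: "the Duration of Surgery as Continuous variable measured in hours", then "the Anastomosis Leakage as Binary variable indicating the presence or absence of leakage", then surgical site infection and local recurrence, both binary. None is called primary. The first aim, at the end of the Background, concerns the effect of temporary ileostomy on leakage.

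Group sizes are in Methodology, Patients: "Patients are assigned to group I (19 patients) who will undergo temporary ileostomy, and group II (28 patients") without. They are not derived from anything. The only leakage rates are in the Background: "The incidence of AL varies from 3 to 21" (per cent). That range is an overall incidence; it is not split by ileostomy status and not linked to the power statement.

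**The concern.** Power is a property of an outcome, a test, a sample size and an assumed effect taken together. The plan gives sample sizes and test families but no effect. A single 80% cannot hold for four outcomes with different, unstated effects, yet the sentence is worded as if it covered every test.

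This matters most for leakage. By the document's own account the value of a protective stoma is debated, so a non-significant result may be read as evidence that ileostomy does not reduce leakage. Someone relying on the stated 80% would put the chance of missing a real difference at 20%. With groups this small and an uncommon event, that chance could be far higher.

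**Working it through.** **Inputs.** Group sizes 19 (ileostomy) and 28 (none), total 47, from Methodology, Patients. Level 5% from the SAP. Sidedness is not stated; two-sided is assumed, since a chi-square test on a 2×2 table is two-sided by construction. No dropout is assumed. Group leakage rates are not given, so values are taken from the 3–21% background range as an assumption. The SAP does not say which version of the chi-square test is meant, so the uncorrected and continuity-corrected versions are both shown, with Fisher's exact test alongside.

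**1. Reproducing the 80%.** This is not possible. No rates, difference, standard deviation (SD) or formula is given for any outcome.

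**2. What counts as significant.** With *a* leaks among 19, *b* among 28 and *m* = *a* + *b*, the uncorrected statistic is

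X² = 47 × [*a*(28 − *b*) − *b*(19 − *a*)]² / [19 × 28 × *m* × (47 − *m*)], significant at 3.84 or more.

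- 0/19 v 5/28: 47 × 95² / (19 × 28 × 5 × 42) = 3.80, not significant.
- 0/19 v 6/28: 47 × 114² / (19 × 28 × 6 × 41) = 4.67, significant.

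So with no leaks at all in the ileostomy group, at least 6 of 28 are needed in the other group (7 by Fisher, 8 with continuity correction). With 1/19 the counts are 8, 9 and 10.

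**3. Exact power.** Power is the sum, over all 20 × 29 possible tables that are significant, of

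C(19, *a*) p₁^*a* (1 − p₁)^(19 − *a*) × C(28, *b*) p₂^*b* (1 − p₂)^(28 − *b*).

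| Leakage with v without ileostomy | Uncorrected chi-square | Fisher | Continuity-corrected |
|---|---|---|---|
| 3% v 21% | 38.4% | 24.8% | 14.1% |
| 21% v 3% (reverse direction) | 50.8% | 41.8% | 33.6% |

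On a grid of all pairs from 3% to 21% in steps of 0.25 points, the second row is the overall maximum and the first is the maximum in the protective direction. At 3% v 21% the test misses the difference 100 − 38 = 62% of the time uncorrected, or 100 − 14 = 86% corrected.

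**4. Rates that would give 80%.** Leakage needed without ileostomy, rounded up to the next 0.1 point:

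| Leakage with ileostomy | Uncorrected chi-square | Fisher | Continuity-corrected |
|---|---|---|---|
| 0% | 26.8% | 30.7% | 34.5% |
| 3% | 32.9% | 36.1% | 39.7% |
| 5% | 37.4% | 39.8% | 43.2% |
| 10% | 46.8% | 49.2% | 51.3% |

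The first entry can be checked directly. With no leaks possible in the ileostomy group, uncorrected power is the chance of 6 or more leaks among 28, which is 80.8% at a rate of 27%. In the reverse direction the smallest difference reaching 80% is 21.2% v 0% by uncorrected chi-square.

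**5. Do those rates fit the background range overall?** Overall incidence is (19 p₁ + 28 p₂)/47. For 0% v 26.8% it is 28 × 26.8/47 = 16.0%. For 3% v 32.9% it is (57 + 921.2)/47 = 20.8%. Both lie inside 3–21%.

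**6. If duration of surgery was meant.** For a t-test with 45 degrees of freedom and non-centrality d × √(19 × 28/47) = 3.364 d, 80% power needs d = 0.851, a difference of about 0.85 SD. The plan states neither a difference nor an SD.

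**The case against.** The plan contains no calculation that could be wrong, so this is an omission and not a proven arithmetic error. The 3–21% is an overall background incidence, and nothing requires both group rates to lie inside it: step 5 shows pairs that reach 80% with an overall rate still in range. Taking leakage as the target is also an inference, because no outcome is primary and duration of surgery is listed first. No decision rule or claim of no effect rests on the 80%, and an observational cohort need not claim any power.

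These points stand as limits. They mean that the 80% is unsupported and not refuted, that the low-power figures are illustrations under assumed rates, and that harm arises only if a reader leans on the figure. They do not rescue the statement. A cohort need not claim power, but this one does, and whichever outcome is chosen the necessary effect is missing.

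One further caution holds. The SAP is partly in the past tense and the group sizes are exact and unequal. If they are realised counts, which the document does not settle, a power sentence would be retrospective, and a detectable difference with a confidence interval would serve better.

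**Conclusion.** The concern holds. That the 80% has no outcome, rates, difference or calculation behind it is certain from the text and needs no assumption. For leakage with 19 and 28 patients, two-sided 5% and group rates confined to 3–21%, power is at most 51%; in the protective direction it is at most 38% uncorrected and 14% with continuity correction. Reaching 80% takes a protective difference of at least about 27 points by uncorrected chi-square, and more by the other two tests. Such a difference is possible, but the plan neither states nor justifies one. The statement should be corrected before any leakage result is interpreted.

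**What to change.** Delete the beta and power figures from the last sentence of the Statistical Analysis Plan and keep the 5% level. Put one of these in their place, with rates and test version chosen and justified by the investigators:

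- *With 19 and 28 patients and a two-sided 5% level, the [named] test has [x]% power for leakage of [a]% with and [b]% without ileostomy.*
- *With 19 and 28 patients and a two-sided 5% level, power of 80% is reached at leakage of 0% with v 27% without ileostomy, or 3% v 33% (uncorrected chi-square).* For Fisher's exact test the rates without ileostomy become 31% and 37%, and with continuity correction 35% and 40% (the step 4 values rounded up to whole per cent).

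The uncorrected version is the most favourable of the three, so the sentence must match the test actually used. If the 80% was meant for another outcome, name that outcome and its assumed difference.

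A useful addition is to report the leakage risk difference with a 95% confidence interval and to say that a non-significant result will not be read as no effect.

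The cost is SAP wording only. The stated power for leakage becomes less favourable; no extra patients are needed and the planned tests do not change.
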